8.4 Study Completion

When an individual subject completes the study, the subject's primary cardiologist will be notified, and the study drug will be stopped; there is no need to wean subjects off of the study drugs. The decision of whether to continue the use of an off label PDE-5 inhibitor for individual subjects will be decided by the subjects and their primary cardiologist, and will be at the subject's expense or that of their third-party payer. Udenafil may also be available to study participants after the conclusion of the study through the manufacturer.

9. SAFETY ASSESSMENTS

9.1 Safety Considerations and Monitoring

The site study coordinators will contact each subject the day after the baseline visit, then weekly for four weeks and monthly until 52 weeks (12 months), and then at 30 and 90 days from the week 52 visit. If the subject is continuing into the extension of up to an additional 36 months then the site study coordinators will contact each subject quarterly until the subject discontinues study drug. At withdrawal or discontinuation, site study coordinators will contact each subject at 30 and 90 days from withdrawal or discontinuation to record adverse events.

9.2. Recording and Reporting Adverse Events

A major component of safety monitoring is ascertainment and reporting of AEs, including adverse drug reactions. The approach to these activities for this study is summarized in the sections that follow.

9.2.1 Definitions of Adverse Event, Suspected Adverse Reaction and Adverse Reaction

[The FDA Final Rule on IND Safety Reporting Requirements](#) provides the following definitions:

- *Adverse event*: any untoward (e.g. unfavorable, negative, or harmful) medical occurrence associated with the use of a drug in humans, whether or not the event is considered drug related. An event can be any unfavorable and unintended sign, symptom, or disease temporally associated with the use of the product.
- *Suspected Adverse Reaction*: any AE for which there is a reasonable possibility that the drug caused the event, meaning the event is possibly, probably related to the study drug.
- *Adverse Reaction*: an AE for which there is a greater degree of certainty regarding causality; meaning the event is probably or definitely related to the study drug. Adverse reactions are a subset of Suspected Adverse Reactions.

9.2.2 Classification of Adverse Events

Monitoring AEs requires that they be classified as to seriousness, expectedness, and potential relationship to the study drugs, all of which drive the reporting process.

a. Seriousness

An SAE is one that:

- Results in death,
- Is life-threatening (the subject was, in the view of the Principal Investigator, in immediate danger of death from the event as it occurred),
- Requires inpatient hospitalization or prolongation of existing hospitalization,
- Results in persistent or significant incapacity or substantial disruption of the ability to conduct normal life functions,
- Is a congenital anomaly/birth defect in the offspring of a participant, or
- Is an Important Medical Event that may jeopardize the subject or may require

medical/surgical intervention to prevent one of the serious adverse event outcomes.

The Common Terminology Criteria for Adverse Events (CTCAE) and MedDRA (<http://ctep.cancer.gov>) provide a grading system and terminology that is used to identify and categorize the severity of adverse events, as follows:

Grade	Severity	Definition
1	Mild	Asymptomatic or mild symptoms; clinical or diagnostic observations only; intervention not indicated.
2	Moderate	Minimal, local or noninvasive intervention indicated; limiting age-appropriate instrumental activities of daily living (ADL).
3	Severe	Severe or medically significant but not immediately life-threatening; Hospitalization or prolongation of hospitalization indicated; disabling; limiting self-care ADL.
4	Life-threatening	Life-threatening consequences; urgent intervention indicated.
5	Death	Death related to AE

An SAE, as defined above, encompasses CTCAE grades 4 and 5, and any Grade 3 event that requires or prolongs hospitalization, or that substantially disrupts the ability of the subject to conduct normal life functions.

b. Expectedness

The purpose of reporting is to provide new, important information on serious reactions or events previously unobserved or undocumented. Therefore, all AEs will be evaluated as to whether their occurrence was unexpected, using the following definitions:

- *Unexpected:* An unexpected AE or adverse reaction is one for which the nature or severity is not consistent with information in the protocol, consent form, or product brochure. An AE or adverse reaction also may be categorized as unexpected if the event has not previously been observed at the same specificity and/or severity. There may be unexpected adverse events in female participants in whom this class of medication has not been extensively studied.
- *Expected:* An event is considered expected if it is known to be associated with the study drug(s) and/or the disease state. According to the product brochure (attached; English translation from Korean) and for this protocol, expected events include:
 - *Spontaneous penile erection*
 - *Facial flushing (> 10%)*
 - *Headache (1-10%)*
 - *Eye redness (1-10%)*
 - *Dyspepsia (1-10%)*
 - *Nasal congestion (1-10%)*

c. Causality

Causality assessment is required to determine which events require expedited reporting. The following criteria will be used to determine causality:

- *Not Related:* The event is clearly related to other factors, such as the subject's clinical state, or non-study drugs or interventions.
- *Possibly Related:* The event follows a compatible temporal sequence from the time of administration of the study drug, but could have been produced by other factors such as the subject's clinical state or non-study drugs or interventions.
- *Probably Related:* The event follows a reasonable temporal sequence from the time of drug administration, and cannot be reasonably explained by other factors such as the

subject's clinical state, or non-study drugs or interventions.

9.2.3 Identification of and Data Collection Procedures for Adverse Events

AEs will be identified when they are reported to the clinical center or during scheduled study visits by study coordinators and investigators. AEs will be assessed using self-report, physical examination data, and medical record review.

9.2.4 Reporting Procedures

Fatal or life-threatening AEs are to be reported to the data coordinating center (DCC) within 24 hours of first knowledge of the event. Those that are unexpected and considered possibly, probably, or definitely related to the study drug (udenafil) will be reported by the DCC to the FDA, the DSMB Chair, the medical monitor (MM), the National Heart, Lung, and Blood Institute (NHLBI), and all study Investigators as soon as possible, but no later than 7 calendar days after first knowledge of the event, followed by a complete report within 15 calendar days. All other fatal or life threatening events that are unrelated to study drug (udenafil) will be reported semiannually to the DSMB and the NHLBI, and annually to the FDA.

Seriousness	Reporting Timeframe	Notification Timeframe
Fatal or life threatening	Within 24 hour of learning of the event	Within 7 calendar days after report
Serious, but not fatal or life threatening, and pregnancy	Within 24 hours of learning of the event	Within 15 calendar days after report
All other	Within 7 calendar days of learning of the event	Within 15 calendar days after report

All other *SAEs (i.e., non-fatal or not life-threatening)* that are unexpected and considered possibly, probably, or definitely related to the study drug will be reported to the DCC within 24 hours of learning of the event. The DCC will report the event to the FDA, NHLBI, DSMB and all study Investigators within 15 calendar days after first knowledge of the event.

All other *AEs* not meeting the criteria for expedited reporting will be reported to the DCC within 7 calendar days of first knowledge of the event. The DCC will report these AEs quarterly to NHLBI and annually to the FDA.

9.2.5 Reporting Adverse Events to Institutional Review Boards for NIH-Supported Multi-Center Clinical Trials

The site Investigator or designee is responsible for reporting all serious adverse events to the local IRB in accordance with local policies and procedures.

A Data and Safety Monitoring Board (DSMB) Summary Report will be prepared within 30 days of each meeting and distributed by NHLBI staff to each Principal Investigator and Study Coordinator. The Summary Report will include information that the DSMB met, they reviewed the study for safety, and which recommendations were made related to the study. The report is to be forwarded to the local IRB.

9.2.6 Follow-up of Subjects after Adverse Events

For AEs with a causal relationship to the study product, follow-up by the Investigator is required until the event or its sequelae resolve or stabilize at a level acceptable to the Investigator.

9.3 Safety Monitoring

The Data and Safety Monitoring Plan for this trial will follow standard PHN monitoring principles. Oversight of data and safety is provided by the PHN DSMB, appointed by NHLBI. The DSMB meets at least twice a year to review data on AEs, adverse reactions, suspected adverse reactions, patient-reported outcomes, data quality, and study recruitment at regular intervals, and makes recommendations about study conduct to the Director of the Division of Cardiovascular Sciences, NHLBI.

The DSMB and NHLBI are assisted by a MM in reviewing serious adverse events in PHN studies. The PHN MM is the NHLBI's designee for determining causality and expectedness of all SAEs.

10. STATISTICS

10.1 Primary Aim - Safety

The primary safety outcome is adverse events. The adverse events will be reported by seriousness, severity and relationship with the study drug. Additionally, the number of subjects experiencing a composite outcome of death, heart failure associated hospitalization, or heart transplant will be reported. The overall assessment of safety will be made on the basis of all available adverse events and safety outcome data over the duration of the 12 months extension trial and an additional 90 days following completion of the study protocol.

10.1.2 Secondary aim – Safety

The secondary safety outcome will be reported similar to Primary safety outcome (see above), but over a longer period of time including additional FU period (i.e. for up to 48 months on the study).

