At Week 52, the subject will undergo testing for primary and secondary efficacy endpoints. Testing for this visit will include an exercise test, an echocardiogram, EndoPAT®, BNP, quality of life questionnaires and safety labs. To minimize any potential effect of the timing of administration of the study drug on testing outcomes, the time of the study drug dosing on the visit day will be standardized. Additionally, if a subject is unable to achieve a maximal effort on exercise testing, they will be offered the opportunity to repeat the EST within two weeks (14 days) of the first test. During this time period, the subject should remain on udenafil. If they achieve a maximal effort on this second study, the results of the second study will be used in the analyses.

At Week 52, vital signs (Resting Blood Pressure/Heart rate) will be obtained; assessment of adverse events, concomitant medications, drug accountability and a blood sample will be drawn for determination of udenafil and metabolite concentration immediately following the exercise test. For female subjects, serum or urine pregnancy test will be administered.

Telephone Contact (Between Baseline and Week 52)

Study coordinators will call each subject the day after drug initiation to ensure the study drug is well tolerated. Subjects will be called at weeks 1, 2, 3, 4, 8, 13, 17, 21, 30, 34, 39, 43, 47 to monitor

adherence, to collect medical history data, and record adverse events through 52 weeks. They will also be called 30 and 90 days after Week 52 to record adverse events. Subjects will be encouraged to notify the study coordinator between scheduled contact dates with any new onset symptoms or complications.

Post-Week 52 Follow-up

Option 1: discontinuation of study drug

If a participant chooses to discontinue study drug after Week 52, a study coordinator will call the subject at 30 (week 56) and 90 days (week 64) to record any additional adverse events possibly or probably related to study drug that may have occurred in the 90 days following completion of the study protocol.

Option 2: continuation of study drug for up to 36 additional months

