Following the Week 52 visit, participants will have the option of continuing on in FUEL-Extension for up to 36 months. During this time, safety data will be collected. Participants will be contacted by the study coordinator on a quarterly basis to monitor and record adverse events. Once study drug has been discontinued (maximum of 36 months following Week 52), subjects will be contacted at 30 days and 90 days following cessation of study drug to monitor for additional adverse events after discontinuation of drug.

For participants who have completed the 24-month extension and have stopped taking study drug for any period of time prior to re-consenting to version 6, the only testing needed prior to re-initiating study drug is a pregnancy test for female participants.

Table 1. Schedule of Events

Visit Number	1	1	TC1	TC 2-15	2	TC 16-17	TC 16 - 28	
Subject Status	New subject (no FUEL)	Former FUEL subject				Post week 52 Option 1	Post Week 52 Option 2	
Time point	Screening/ Baseline Day 0	Screening/ Baseline Day 0	Day 1	Weeks 1, 2, 3, 4, 8, 13, 17, 21, 30, 34, 39, 43, 47	Week 52	Day 30, 90 post-study (Weeks 56 and 64)	Quarterly	Day 30, 90 post-drug discontinue
Visit Window(s)				± 3 days	± 10 days	± 10 days		
Type of Visit(s)	In-Person	In-Person	Call	Calls*	In-Person	Calls	Calls	Calls
Informed Consent/Assent	X	X						
Subject ID# assigned	X							
Inclusion/Exclusion Criteria	X							
Physical Measurements	X							
Medical history	X							
Demographics/expanded demo	X							
Prior/Concomitant Meds	X			X	X			
EndoPAT®	X				X			
Serum or urine pregnancy test	X	X			X			
Clinical Laboratory tests (creatinine, ALT, AST)	X				X			
Biomarker (BNP) sample	X				X			
Genetic repository sample (optional)	X							
Heart Monitor (optional)	X							
Echocardiogram	X				X			
Exercise test (EST)	X ^a				X ^a			
Dispense Open Label Udenafil ^b	X	X						
Resting BP and HR ^c	X	X			X			
Administer first dose of study drug ^c	X	X						
Peds QL generic and cardiac modules; PCQLI; HAES	X				X			
Drug Accountability ^b	X				X			
Pregnancy counseling (if appl)	X	X		X				
Adverse events assessment		X	X	X	X	X	X	X
Morisky Scale (MMAS)				X				
Schedule/Confirm next visit	X	X	X	X	X			

^a If failed 1st exercise test, exercise testing can be repeated w/in 14 days. Pregnancy testing must also be repeated.^b For detailed Drug Accountability procedures, consult the Manual of Operations (MOO)^c For specific timing of procedures, see Additional Procedures and Measurements in Table 2

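### Section 10.1.2 carries the 12-month safety counts to 48 months although follow-up after Week 52 is optional, so the pooled count is neither a fixed-time risk nor a rate and Aim 5 gets no figure of its own

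*Combined protocol and SAP*

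**What the plan says.** Section 10.1 reports adverse events by seriousness, severity and relationship to drug. It adds that "the number of subjects experiencing a composite outcome of death, heart failure associated hospitalization, or heart transplant will be reported". The primary window is "over the duration of the 12 months extension trial and an additional 90 days following completion of the study protocol".

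Section 10.1.2 is the whole plan for the longer period: the secondary safety outcome "will be reported similar to Primary safety outcome (see above), but over a longer period of time including additional FU period", for up to 48 months.

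Section 6.4 makes the time after Week 52 elective. Those who stop have calls at 30 and 90 days (weeks 56 and 64). Otherwise, "participants will have the option of continuing on in FUEL-Extension for up to 36 months", and "Participants will be contacted by the study coordinator on a quarterly basis to monitor and record adverse events". Calls at 30 and 90 days then follow the end of drug. The same section allows for participants who completed the 24-month extension and "have stopped taking study drug for any period of time prior to re-consenting to version 6".

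Secondary Aim 5 (Section 4.2) concerns safety in the additional period, among those who opt in. For safety, Section 10 specifies no person-time, no interval estimate, no split by drug status and no separate summary after month 12.

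**The concern.** In the primary window planned follow-up is nearly uniform, so a number of subjects set against the number enrolled is close to a risk. That no longer holds once each participant decides how long to stay. Planned contact ends about 15 months after entry for someone who stops at Week 52, and about 51 months after entry (48 plus the 90-day calls) for someone who takes the full option.

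The reported figure then depends on how many people continued as well as on how often events occur. It also mixes year 1 with the added years, which exist to provide longer-term safety data. Subtracting the primary count does not repair this: the primary window includes a 90-day tail, so what is left starts at about month 15 and has no exposure attached. A change in event frequency after the first year could go unseen.

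**Working it through.** The plan gives no event rate, precision or continuation rate for safety, so there is no figure of its own to reproduce. The calculation below is an illustration.

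**Inputs.** From the documents: N = 300 (the minimum in Section 6.1). Assumed:
- 10% lost evenly over year 1, with no tail for them;
- the same share p continuing at months 12, 24 and 36;
- 90 days observed after stopping (90/365.25 = 0.2464 years), with follow-up cut at month 48;
- no stops or pauses within a year, and no truncation at the event;
- 12 subjects with the composite.

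**Person-years.** Year 1: 300 × (1 − 0.10/2) = 285. Subjects at month 12: 270. On-drug time in years 2, 3 and 4: 270p, 270p², 270p³. Off-drug tails: 270(1 − p)(1 + p + p²) × 0.2464.

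| p | On-drug person-years, years 1 to 4 | Tails | Total | 12 events per 100 person-years (exact 95% CI) |
|---|---|---|---|---|
| 0 | 285, 0, 0, 0 | 66.5 | 351.5 | 3.41 (1.76–5.96) |
| 0.5 | 285, 135, 67.5, 33.8 | 58.2 | 579.5 | 2.07 (1.07–3.62) |
| 0.8 | 285, 216, 172.8, 138.2 | 32.5 | 844.5 | 1.42 (0.73–2.48) |
| 1 | 285, 270, 270, 270 | 0 | 1,095 | 1.10 (0.57–1.91) |

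The planned output is 12 in every row. Changing year-1 loss to 5% or 20% moves the p = 0.5 rate only to 1.99 or 2.26, and the p = 0.8 rate to 1.36 or 1.56.

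**Masking of timing.** At p = 0.8, year 1 supplies 285/844.5 = 34% of the time, leaving 559.5 person-years later.
- 9 early and 3 late: 9/285 = 3.2 and 3/559.5 = 0.5 per 100.
- 3 early and 9 late: 3/285 = 1.1 and 9/559.5 = 1.6 per 100.

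Both give the same pooled count.

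**Late precision.** With zero events the two-sided 95% upper limit is 3.69 divided by person-years. Year-4 on-drug time is 34 (p = 0.5) or 138 (p = 0.8) person-years, giving limits of 10.9 or 2.7 per 100. Adding the tails of those who stop at month 36 (8.3 or 8.5) gives all observed year-4 time of 42 or 147, with limits of 8.8 or 2.5.

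**Off-drug share.** 58.2/579.5 = 10% and 32.5/844.5 = 4%. These are minimum values under this model, because Section 7.4 allows temporary and permanent stops while subjects stay in the trial and Section 6.4 describes gaps before re-consent.

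**Check with a constant hazard.** Assume instead a 12-month risk of 5%, so λ = −ln(0.95) = 0.0513 per year, with a share c followed for 4 years and the rest for 1.25 years. The expected proportion is (1 − c)(1 − e^(−1.25λ)) + c(1 − e^(−4λ)) = 0.0621(1 − c) + 0.1855c. It is 9.3%, 12.4%, 15.5% or 18.5% at c = 25%, 50%, 75% or 100%. The 48-month risk is 18.5% and the rate 5.13 per 100 person-years throughout.

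**The case against.** This is a single-arm, descriptive, opt-in secondary summary with no safety hypothesis test, and Section 14 describes the study's safety evaluation as covering one year. That limits the weight of the point. But where nothing is tested, the descriptive figure is the result, so it should be interpretable.

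The 3.4 to 1.1 spread comes from holding the count at 12 while person-time triples; under a steady hazard the count would rise with uptake. That is fair. The constant-hazard check meets it: the count does rise, but the proportion it implies equals the 48-month risk only if everyone continues.

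Section 7.5 plans to keep ascertaining death, hospitalization and major complications in subjects who withdraw, and Section 11 captures censoring and loss data. This softens the concern for withdrawals and makes person-time obtainable. It does not extend planned contact for those who complete Week 52 and stop.

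A reader might infer that the plan will understate the 48-month risk by a known amount, for example 12.4% against 18.5%. The documents do not support that. They give neither an event rate nor an uptake, and Section 10.1 promises a number of subjects, never a proportion.

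**Conclusion.** The point stands as an analysis choice worth improving. The pooled count over up to 48 months mixes follow-up of very different lengths, is neither a fixed-time risk nor a rate, and leaves Secondary Aim 5 without a matching output. Under the stated assumptions the same 12 subjects could mean anything from 1.1 to 3.4 per 100 person-years. The true size depends on uptake and event rates that the documents do not give.

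Two further inferences go too far. One is that the protocol contains a wrong figure; it does not. The other is that the 90-day tail must run from Week 52 for everyone. Section 6.4 says of the subjects called up to Week 52, "They will also be called 30 and 90 days after Week 52 to record adverse events", and Section 9.1 also counts from the Week 52 visit, but Section 6.4 (Option 2) and Section 6.5 count from the end of drug. The anchor for continuers is open.

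Two other inconsistencies bear on the remedy. Aim 5 gives its period as months 12–36 and also as up to an additional 36 months, while Section 10.1.2 says 48 months in all. And Option 1 describes its calls as made "to record any additional adverse events possibly or probably related to study drug", as does Section 6.5 in similar terms, whereas Sections 6.3.1, 6.4 (Option 2) and 9.1 set no such limit. The second is a data-collection matter, but until it is settled a low off-drug event rate could reflect recording alone.

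**What to change.** Keep the counts and add to Section 10.1.2:

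- Incidence per 100 person-years with 95% confidence intervals for the composite, serious adverse events and adverse events, over all observed follow-up and over on-drug time derived from the stops and restarts recorded under Section 7.4. Unobserved gaps before re-consent should not count as follow-up.
- A separate summary of the period after month 12 in subjects who continue, with its own person-time, stating that it overlaps the 90-day tail of the primary window.
- A statement that continuation is self-selected, that late estimates are imprecise, and that scheduled calls fall from 14 in year 1 (the day after initiation plus 13 listed weeks) to quarterly, so rates of non-serious events are not directly comparable between periods.

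Reconcile, without presuming the answer: the anchor of the 90-day tail for continuers (Sections 10.1, 6.4, 6.5, 9.1); the end of the Aim 5 period (Sections 4.2, 10.1.2); and whether post-drug calls record all adverse events or only those possibly or probably related (Sections 6.3.1, 6.4, 6.5, 9.1). If only related ones, do not report all-event rates for off-drug time.

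The cost is analysis wording, a few more tables and wide late intervals. The stop, restart and loss data are already to be captured. Off-drug events may be under-ascertained in data already collected, and new tables cannot recover them.

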Significance	The Fontan Udenafil Exercise Longitudinal Study is planned to evaluate the efficacy and safety of udenafil over a six-month period. However, an understanding of the longer-term safety profile of udenafil is critical prior to adopting it for use in those with Fontan physiology.
Study Design	Open label extension trial of udenafil (87.5 mg twice daily).
Primary Safety Measurements	Safety will be assessed by monitoring adverse events and vital signs, clinical laboratory test results, 12-lead ECG, and physical examinations.
Other Safety Measurements	
The effect of treatment on the functional health status in adolescents following a Fontan procedure.
 
The effect of treatment on the prevalence and severity of complications, including protein-losing enteropathy (PLE), plastic bronchitis, hospitalizations, cardiac transplantation, and death in adolescents who receive udenafil following the Fontan procedure.

Efficacy Measurements	Evaluate the effect of udenafil on pharmacodynamic outcomes including exercise capacity, echocardiographic measures of ventricular function, endothelial function, and serum biomarkers, as well as measures of functional health status / quality of life. Explore the impact of udenafil on atrial and ventricular premature beats and arrhythmia burden – optional for a subset of new participants.
Sample Size	All subjects enrolled in FUEL trial, with minimum of 300 subjects
Study Duration	Approximately 12-15 months (recruitment plus study procedures and follow up phone calls). Participation in the trial may be extended up to an additional 36-39 months for those opting to continue for additional follow-up (includes 3 months of follow-up after last study dose).

Inclusion Criteria	
 1. Males and females with Fontan physiology who participated in the FUEL trial or, if they did not participate in FUEL, those who are 12 to less than 19 years of age at enrollment. 2. Participant consent or parental/guardian consent and participant assent. 3. Participant fluent in English, Spanish, or Korean 4. Current anti-platelet or anticoagulant therapy

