6. STUDY / TRIAL DESIGN

6.1 Overview

This study is a 12-month (52 week) safety extension study, with an option for up to an additional 36 months, to supplement the FUEL Phase III clinical trial to provide a more robust safety and side-effect profile of the use of udenafil in adolescents with Fontan physiology. We will attempt to recruit all participants who completed the FUEL trial, a potential of approximately 400 subjects, and will supplement, if needed, with additional adolescents with Fontan physiology until the minimum of 300 total subjects have been enrolled.

Figure 1 Trial Schema

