6.5 Data Collection

1. Demographic information

The following demographic data will be collected: age, gender, race, ethnicity, cardiac anatomy, date of Fontan, presence of a fenestration, degree of atrioventricular valve regurgitation, grade of ventricular function, concomitant medications, and significant comorbidities.

2. Safety data

Adverse events will be reviewed with each subject at each study visit and during telephone encounters. These events will be recorded and graded by severity and relationship to study drug based on established criteria. Two additional telephone encounters will take place 30 days and 90 days following cessation of study drug [either at Week 52 or up to Week 208 if the subject opts to continue study drug] to assess for any adverse events possibly or probably related to study drug in the period following the completion of study procedures.

3. Exercise stress test

Data from the braked cycle ergometry exercise stress tests will be collected according to protocol established in the PHN Fontan Cross-Sectional Study³.

4. Assessment of ventricular performance

Each study echocardiogram will be stored in a de-identified manner and sent to a core laboratory, which will perform the data analysis and submit the measurements to the PHN Data Coordinating Center (DCC).

5. Vascular function testing

De-identified data from EndoPAT® testing will be collected according to a standardized protocol. These data will be sent to a vascular core lab, which will perform the analysis and submit the measurements to the PHN DCC.

6. Biomarkers

Serum for measurement of BNP level will be sent to a core clinical lab. Results will be sent directly to the PHN DCC.

7. Quality of life survey

Results of the Quality of life surveys will be submitted to the PHN DCC.

8. Samples for the biorepository

Samples collected for the biorepository will be shipped directly to the biorepository for future analysis.

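### Section 10.1.2 ends the long-term safety window at 48 months on study, which is the maximum time on drug, and leaves out the 90-day post-drug period that the rest of the protocol schedules

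*Combined protocol and SAP*

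**What the plan says.** **Analysis windows.** Section 10.1 assesses primary safety "over the duration of the 12 months extension trial and an additional 90 days following completion of the study protocol". Section 10.1.2 refers back to that rule for its reporting (the long-term outcome "will be reported similar to Primary safety outcome (see above") and then sets a different period of its own: "over a longer period of time including additional FU period (i.e. for up to 48 months on the study". It does not mention the 90 days.

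**Time on drug.** Section 6.1: "This study is a 12-month (52 week) safety extension study, with an option for up to an additional 36 months". Section 6.5 puts the last possible stop in weeks: "either at Week 52 or up to Week 208 if the subject opts to continue study drug".

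**Follow-up after the drug.** For subjects who continue past Week 52, Section 6.4 (Option 2) says that "subjects will be contacted at 30 days and 90 days following cessation of study drug to monitor for additional adverse events after discontinuation of drug". Section 9.1 schedules the same two contacts after any withdrawal or discontinuation.

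**Total duration.** The synopsis (Section 2, Study Duration) says: "Participation in the trial may be extended up to an additional 36-39 months". It adds that this range contains the 3 months of follow-up after the last dose.

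**Secondary Aim 5.** Section 4.2 gives the horizon of this aim as study months 12 to 36, next to an opt-in of up to 36 further months on drug.

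**The concern.** The data-collection sections and the analysis section end at different times. Sections 6.4, 6.5, 9.1 and the synopsis all follow a subject for 90 days past the last dose. Section 10.1.2 stops at the month in which the longest-treated subjects take their last dose.

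Applied as written, the limit makes inclusion of post-drug events depend on how long the subject was treated. A subject who stops at month 24 has all 90 post-drug days in the summary, and one who completes the full course has none. The subjects who lose follow-up are those with the longest exposure. Section 10.1 also reports the composite of death, heart-failure hospitalization and transplant, and Section 10.1.2 follows its reporting, so late composite events could be left out along with other adverse events.

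Even if nobody intends this, whoever programs the summary has to choose between two cut-offs, and the choice could be made after the late events are known.

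**Working it through.** **Inputs**
- Core period 12 months, optional period up to 36 months (Section 6.1)
- Last possible stop Week 208 (Section 6.5)
- Contacts 30 and 90 days after the last dose (Sections 6.4, 6.5, 9.1)
- Synopsis extension 36 to 39 months, including 3 months after the last dose
- One month taken as 365.25 / 12 = 30.44 days

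**1. Where the plan's 48 comes from.** 12 + 36 = 48 months, and 208 / 52 × 12 = 48.0 months. The stated limit therefore equals the maximum time on drug, with no post-drug time in it.

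**2. When follow-up ends for a full-course subject.**
- 30-day contact: 48 + 30 / 30.44 = month 49.0 (208 + 30 / 7 = Week 212)
- 90-day contact: 48 + 90 / 30.44 = month 51.0 (208 + 90 / 7 = Week 221)
- Synopsis check: 39 − 3 = 36 months on drug, and 12 + 39 = 51 months in total. The two routes agree.

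**3. The parallel with Section 10.1.** The primary window is 12 + 90 / 30.44 = 15.0 months. Built the same way, the long-term window would be 48 + 90 / 30.44 = 51.0 months.

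**4. Who is affected on the literal reading.** The full 90 days fit inside the limit only if drug stops by 48 − 90 / 30.44 = month 45.0. The 30-day contact fits only if drug stops by 48 − 30 / 30.44 = month 47.0. For a stop at month *s*, the post-drug days inside the window are (48 − *s*) × 30.44, limited to the range 0 to 90:

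| Stop at month | Post-drug days inside | Share of 90 |
|---|---|---|
| 24 | 90 | 100% |
| 45 | 90 | 100% |
| 46 | 61 | 68% |
| 47 | 30 | 34% |
| 48 | 0 | 0% |

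**5. What cannot be computed.** The documents do not say how many subjects stop after month 45, and they give no event rate for the post-drug period. No count of lost events follows from them. For one full-course subject the 90 days are 90 / (1,461 + 90) = 5.8% of total follow-up, but that is a share of calendar time and not of events.

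**The case against.** **The primary rule may carry over.** Section 10.1.2 points back to Section 10.1, which takes all available safety data and adds 90 days. One can read it as replacing 12 months with 48 and keeping the rest. The protocol also labels periods by treatment length elsewhere: the Primary Aim is stated over 12 months, yet its analysis runs to 12 months plus 90 days. This reading is plausible, and no section says outright that events after month 48 are dropped. A reader might therefore infer too much by treating the exclusion as the sponsor's settled rule. It is the literal result of the wording and does not prove intent. The objection does not rescue the wording, however: the sentence contrasts its period with the primary one and then defines it in months on study, and time on study reaches month 51.

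**Purpose of the fourth year.** A reader might also infer that the fourth year was added in order to observe the longest-exposed subjects. The documents do not say so. The amendment log gives the reason as subjects' interest in staying on drug and ties more robust safety data to the second and third years.

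**Limited consequence.** The summary is descriptive, with no test, threshold or formal stopping rule attached. Post-drug events are still collected, reported under Section 9.2.4 and open to review by the DSMB, which meets at least twice a year. Section 6.5 also limits the purpose of the two calls to events possibly or probably related to drug, although Sections 6.4 (Option 2) and 9.1 set no such limit. All of this stands. It bounds the harm but does not make the limit correct.

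**Conclusion.** The point holds as a defect in the wording of the analysis window and should be corrected. Section 10.1.2 states a limit of 48 months on study where the protocol's own schedule runs to about month 51.

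On the literal reading, the loss rises from none for a stop at about month 45 to all 90 days for a stop at month 48, so it falls only on the longest-exposed subjects. On the reading that carries the 90 days over, nothing is lost, but the stated number is still wrong. The month figures assume 30.44 days per month; with 52-week years the end of follow-up is still about month 51.

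The documents do not support a claim that events go uncollected or unreported, or that any particular number of events is missing.

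**What to change.** In Section 10.1.2, replace the parenthesis with wording such as: *all available follow-up, including the 90 days after the last dose (up to 48 months of treatment, about 51 months on study)*.

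The phrase *all available follow-up* is needed. Section 7.4 keeps subjects in the trial after they stop drug, so a window that simply ended 90 days after the last dose could truncate early stoppers who are still being followed.

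In the same edit, reconcile the month 12 to 36 horizon in Secondary Aim 5 (Section 4.2) with the optional period of up to 36 further months and with Section 10.1.2. Otherwise the aim and its analysis will still name different periods.

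The cost is one sentence in Section 10.1.2 and one figure to reconcile in Section 4.2. No new data are needed, because the contacts are already scheduled. The summary may count a few more events.
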